16. DATA AND SAFETY MONITORING PLAN

Risk to study subjects is minimized by only employing well-trained and clinically experienced personnel. Routine hospital protocols are already in place for handling in-person and over-the-phone crises.

Adverse Events (AEs) and Serious Adverse Events (SAEs)

An adverse event is "any untoward or unfavorable medical occurrence in a human subject...temporally associated with the subject's participation in the research, whether or not considered related to the subject's participation in the research." A serious adverse event (SAE) is an event where a relationship to the research study cannot be ruled out, and the event is life-threatening/results in death OR disabling/incapacitating OR requires or prolongs hospitalization OR involves an overdose OR was otherwise unanticipated, related to the study procedures. Due to the nature of this study, suicide attempts and psychiatric hospitalizations are possible to

happen during its course. These events are considered SAEs and reported as such. In most circumstances, suicide attempts and psychiatric hospitalizations are expected for this population and, as a result, non-study related. As such, these SAEs will be reported at continuing review but only unexpected reported immediately to the IRB. Suicide deaths are reported to the IRB within 48 hours of learning of the death. In addition, the report includes investigators' judgment as to whether a relationship to the research study can/cannot be ruled out.

For all AEs, the date and time of onset and outcome, course, intensity, action is taken, and causality to study treatment will be assessed. Based on the review of the circumstances and as-needed consultation with co-investigators, the PI can reclassify an AE as an SAE. If considered related to the study, unanticipated adverse events involving risks to subjects or others will be reported by the PI to IRB. For each adverse event, the treatment groups are compared in a pair-wise fashion regarding the occurrence of at least one event using Fisher's exact tests; the numbers of individual events will also be described. All subjects are included in these analyses.

Confidentiality

There will be a restriction from unauthorized access to identifiable subject data, storage of data to protect against the inadvertent loss, and use of appropriate database software tools to maintain the integrity of data for subsequent analyses. All research files are coded using a study identification number. Subject identifying information and PHI are marked with REDCap's "identifier" designation so it is automatically removed from any data exports. Additionally, access to any forms containing identifying or protected health information is only granted to those investigators, clinicians, or staff who need this information to conduct the study. All identifying data is stored in locked cabinets, offices, or password-encrypted files. Access to these files is limited to investigators and support personnel with the need to enter or analyze data.

Data sharing agreement will involve sharing only de-identified data with other investigators and the use of data-sharing agreements that provide for: (1) a commitment to using the data only for research purposes and not to identify any individual subject; (2) a commitment to securing the data using appropriate computer technology; and (3) a commitment to destroying or returning the data after analyses are completed.

All research and clinical information obtained is confidential unless the subject is an immediate danger to themselves or others. Subject well-being will be carefully monitored throughout the study. If the clinical information obtained in the course of research assessments pertains to subject safety (e.g., intent to harm oneself or others), then confidentiality is not maintained, and appropriate treating professionals will be informed. During crisis situations, this clinical information may be provided to other clinicians (or family members) to facilitate appropriate treatment and minimize the risks of self-harm or harm to others. This information may include the subject's medical history, financial and social resources, and history of suicidal behavior if known.

Certification of Research Personnel in the Protection of Human Subjects

To ensure appropriate human research knowledge, all study personnel interacting with subjects or with access to subject research have completed mandatory training in the protection of human research subjects per guidelines issued by the U. S. Department of Health and Human Services, Office for Human Research Protections (see http://ohrp.osophs.dhhs.gov/) and per guidelines of the URMC. Any additional personnel will complete this training before interacting with study subjects. Consistent with RSRB policy, all investigators and research staff will complete

certification by the RSRB—required completion of a course that contains seven modules dealing with topics such as "Ethics and Federal Regulations," "Roles and Responsibilities of the Investigator and the Study process," and "Roles and Responsibilities of Institutions in Human Subjects Research," among others. The program provides a substantial resource to the investigator for understanding the ethics and regulations governing research with human subjects.

ClinicalTrials.gov Requirements

In line with NIH recommendations, our trial was registered with clinicaltrials.gov (NCT05280756).

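### Section 16 makes possible relatedness a condition of being an SAE, contradicting its own later sentences and leaving some serious events without the label

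*Combined protocol and SAP*

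**What the plan says.** Everything at issue stands in Section 16, under the adverse event subheading.

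- An adverse event is defined independently of cause: it counts "whether or not considered related to the subject's participation in the research".
- The SAE definition opens with a causality condition: "A serious adverse event (SAE) is an event where a relationship to the research study cannot be ruled out". A conjunction ties this to a list of alternative outcomes: a fatal or life-threatening course, disability, hospitalization and overdose. The list closes with "OR was otherwise unanticipated, related to the study procedures".
- Of suicide attempts and psychiatric hospitalizations the paragraph says: "These events are considered SAEs and reported as such". It adds that, in most circumstances, "suicide attempts and psychiatric hospitalizations are expected for this population and, as a result, non-study related". On reporting: "As such, these SAEs will be reported at continuing review but only unexpected reported immediately to the IRB".
- Suicide deaths go to the IRB within 48 hours. The next sentence says that "the report includes investigators' judgment as to whether a relationship to the research study can/cannot be ruled out".
- For every adverse event the plan assesses onset, outcome, course, intensity, action taken and causality. The principal investigator may upgrade an adverse event to an SAE. Unanticipated adverse events go to the IRB if considered related.
- The arms are compared separately for each adverse event, on whether a subject had at least one, by Fisher's exact test in all subjects. No comparison or table of SAEs by arm is specified.

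**The concern.** Seriousness describes what happened to the subject. Causality is an opinion about why, and expectedness is a third matter. The definition folds all three into one label. A grave event can lose the label because someone rules out a link to the study, and a trivial event can gain it because it was unforeseen and procedure-related.

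At stake is whether the SAE listing from this trial can be read at face value. Section 2 says that, to the authors' knowledge, tDCS has not been studied as an adjunct for suicidal ideation or behavior, so later trials are likely to look at this listing. If the label depends partly on causality opinion, and staff must choose between a definition and later sentences that disagree with it, two people applying Section 16 in good faith could produce different SAE lists from the same events.

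**Working it through.** The plan states no SAE count or rate, so there is no figure to reproduce. The check is to apply Section 16 to each kind of event.

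**Step 1: the contradiction.** The definition requires that a relationship cannot be ruled out. Suicide attempts and psychiatric hospitalizations are declared SAEs, and in most circumstances presumed unrelated to the study. Where a relationship is in fact ruled out, the definition removes the label and the later sentence restores it. The sentence asking for a can/cannot judgment points the same way, since it treats causality as something recorded about an event already being reported. It follows the suicide-death rule and may refer only to those reports, so it is supporting evidence. The contradiction over the two named event types does not depend on it.

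**Step 2: what each rule does.** The first three rows assume that the relationship has been ruled out.

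| Event | SAE by the definition? | SAE by a later sentence? | IRB route stated in Section 16? | In the per-event Fisher comparison? |
|---|---|---|---|---|
| Suicide attempt, psychiatric hospitalization | No | Yes | Yes: continuing review, or at once if unexpected | Yes |
| Suicide death | No | Not addressed | Yes: within 48 hours | Yes |
| Medical hospitalization, disabling event, other life-threatening event, non-suicide death | No | No | None | Yes |
| Mild, unanticipated, procedure-related event (relationship not ruled out) | Yes, by the last item | Not needed | Yes: related and unanticipated | Yes |

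The third row is the gap. Such an event is not one of the two named types, is not a suicide death, and fails the remaining rule because that rule needs a judgment that the event is related. The fourth row is the reverse fault, because the last item sets no threshold of seriousness.

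**Step 3: can the event be found again in the data?** The attributes listed for all adverse events do not include seriousness. Intensity is a different attribute. Outcome and action-taken entries may reveal a hospital stay or a death, but no stated field marks the event as serious. Because the comparison is made event by event, different serious medical events may be spread over several terms and never be seen together.

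**Step 4: scale.** Section 4 gives 20 subjects, randomized 1:1. If the split is even, 20 / 2 = 10 per arm, and one subject is 1/10 = 10 percentage points in any SAE table by arm. This shows how much one classification decision would weigh in such a table. It does not estimate how many events are affected.

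**The case against.** Four points can fairly be made for the plan.

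1. The serious events it expects in this population are expressly kept as SAEs, and suicide deaths have their own deadline. This stands, and it confines the gap to the third row of the table.
2. Causality is already collected for every adverse event, and the stated discretion over SAE status runs only upward. The first part stands and makes the fix cheap. The second helps little: no criteria are given for upgrading, so it adds a further judgment.
3. The bar is low. An event escapes only if a relationship is ruled out, not merely thought unlikely, and the last item widens the class, which is cautious. This reduces how often the gap will matter but does not close it.
4. The chain of alternatives could be parsed so that the causality condition applies only to death and life-threatening events. The grammar favors applying it to the whole list, since all the alternatives share one subject. On the other parse, an unrelated death still falls outside while an unrelated hospital stay falls inside, which is no better.

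Two stronger readings are tempting, and the documents support neither. A reader might infer that every serious event judged unrelated ceases to be an SAE; the sentence on suicide attempts and psychiatric hospitalizations says otherwise. A reader might also infer that causality opinion could hide an imbalance between arms in the planned safety analysis. The planned comparison uses adverse events, which are counted whatever their cause, so these events stay in it, and no SAE-by-arm comparison is planned. Nor do the documents give a reason to expect a one-sided filter: Section 4 describes the trial as double-blind, and Section 8 assigns randomization and device set-up to staff outside supervision and assessment.

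**Conclusion.** The point holds as a fault in the definition. Section 16 makes possible relatedness a condition of the SAE label and contradicts this a few sentences later. Taken literally, it leaves serious events other than suicide attempts, psychiatric hospitalizations and suicide deaths without an SAE label, an IRB route in that section or a seriousness flag once a relationship is ruled out. Its last item also labels some events as SAEs without regard to seriousness.

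The damage is to SAE classification, SAE reporting and any SAE summary. The primary feasibility outcome and the planned adverse event comparison are untouched. The number of events affected is unknown, because the plan gives no expected rate, and in 20 subjects it may be none. The conclusion rests on reading the definition as written and on Section 16 containing all the reporting rules; institutional policy outside the documents might supply a route. The change is worth making because it is small and removes a real ambiguity in safety reporting.

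**What to change.** Rewrite the definition and align the sentences that follow it:

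- Define an SAE as any adverse event meeting one of the listed outcome criteria, whatever its relationship to the study. This agrees with the later treatment of suicide attempts and psychiatric hospitalizations.
- Keep causality as its own field, as already planned for all adverse events, and add two fields: seriousness (with the criterion met) and expectedness.
- Move the closing item on unanticipated, procedure-related events to the rule on reporting unanticipated events to the IRB.
- State the IRB route for SAEs other than the two named types and suicide deaths. The continuing-review sentence refers to the named types, so a wider definition alone would not supply one.
- Add a table of SAEs by arm regardless of relatedness, with causality shown alongside.

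The cost is a one-paragraph amendment, two form fields and one descriptive table. Treatment, sample size and the primary outcome do not change. The downside is that slightly more events will carry the SAE label.

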4. STUDY DESIGN

This is a single-center, randomized, sham-controlled, double-blind clinical study to investigate the feasibility of delivering RS-tDCS sessions for high-risk patients for suicide in the days following discharge from the CPEP or inpatient unit which they were admitted with SI or attempt. We plan to assess up to 80 adult patients for eligibility over 12 months of which 20 will be enrolled and randomized. Clinical assessments will be performed at baseline, post-treatment day 14 (14 days after the first RS-tDCS session), and follow-up day 30 and 60 (30 and 60 days after the first RS-tDCS session, respectively).

All study outcome measures are described in Table 1.

Time points		in-person	remote	
	Measures		S1 to S10	C14, C30, and C60
Eligibility screening		Х		
Informed consent		Х		
Enrollment		Х		
		Baseline		
Demographic data		Х		
General medical history		X		
Orientation tDCS session		X		
Loan agreement		Х		
	Feasibility		X*	
	C-SSRS	X		Х
	RRS	X		Х
	CAST	Х		Х
	MADRS	Х		Х
	C-SSRS SV		X	
	Side effects questionnaire		X	
	Treatment emergent event review		Х	Х
	Acceptability questionnaire		X**	
	Blinding assessment		X**	

Table 1. Study's time points and measures.

C14, C30, and C60: clinical assessments at post-treatment day 14, follow-up day 30 and follow-up day 60; CAST: The Concise Associated Symptoms Tracking; C-SSRS: The Columbia-Suicide Severity Rating Scale; C-SSRS SV: The Columbia-Suicide Severity Rating Scale – screening version; MADRS: Montgomery-Asberg Depression Rating Scale; RRS: Ruminative Responses Scale; S1 to S10: remotely supervised transcranial direct current stimulation (RS-tDCS) sessions one to ten.

*Number of completed RS-tDCS sessions per participant within three weeks of the study.

**applied only once, after the final RS-tDCS session (the tenth session).

Primary outcome measures:

Page 5 of 22 Version Date: 10/09/2023 1. Feasibility of the intervention – number of completed remotely supervised transcranial direct current stimulation (RS-tDCS) sessions, for both active and sham groups:

We expect at least 70% of the subjects to complete at least 5 of recommended 10 RS-tDCS sessions within three weeks of receiving the home-based tDCS device.

This criterion is based on a study that reported dropout rates between 22% and 25% of homebased tDCS for patients with bipolar depression (40) and that therapeutic effects with tDCS could be achieved within one week of treatment (24).

Secondary outcome measures:

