Subjects will be randomized 1:1 to either active or sham RS-tDCS. The active RS-tDCS delivers a constant current intensity of 2mA on the subject's scalp, with SNAPstrap headgear and 5x7 (35cm2) SNAPpads positioning bilaterally (anodal-left and cathodal-right), on the DLPFC, for 30 minutes. A similar protocol's administration was found effective, safe, and tolerable as an add-on intervention to decrease depressive symptoms in patients with bipolar depression (45). Sham tDCS looks identical to a typical RS-tDCS cap but delivers a 30-second ramp-up (0-2 mA) stimulation followed by a 30-second rampdown (2-0 mA) at the beginning and end of the application. Figure 2 shows a representation of the electric current delivered by the active and sham RS-tDCS.

[figure not shown]

Figure 2. Stimulation protocol. Active tDCS (upper) and sham tDCS (lower).

The tolerability and safety of home-based tDCS were assessed over 6,779 sessions from six clinical trials. Sessions were administered daily, with treatment ranging from 10 to 60 sessions per subject. The authors reported no serious adverse events, a similar proportion of tingling (68%), itching (41%), and warmth sensation (42%) between active and sham groups, and no participant discontinuation due to lack of tolerability (39).

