17. DATA ANALYSIS PLAN

To assess feasibility, the primary outcome of this study, we chose a sample size of 20. To infer feasibility, at least 50% of the sessions should be performed successfully per subject for at least 70% of the subjects. This criterion is based on a study that reported dropout rates between 22% and 25% of home-based tDCS for patients with bipolar depression (40) and that therapeutic effects with tDCS could be achieved within one week of treatment (24). For each time point established, we will compare groups with a t-test or chi-square test, for continuous and categorical data, respectively (a p value<0.05 will be considered significant).

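### At about 10 subjects per arm, the per-event Fisher's exact test says almost nothing about comparative safety, and Section 16 plans no estimate or interval beside it.

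*Combined protocol and SAP*

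**What the plan says.** Section 16 (Data and Safety Monitoring Plan, adverse events) gives one between-arm rule for adverse events: for each event, "the treatment groups are compared in a pair-wise fashion regarding the occurrence of at least one event using" Fisher's exact tests. It adds that the numbers of individual events will be described and that "All subjects are included in these analyses". It states no significance level, sidedness, multiplicity rule, effect estimate or interval for these tests, and does not say how a non-significant result is to be interpreted. The same section classes suicide attempts and psychiatric hospitalizations as serious adverse events.

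The group sizes come from Section 4, where up to 80 patients are assessed, "of which 20 will be enrolled and randomized", and from Section 4.1: "Subjects will be randomized 1:1 to either active or sham RS-tDCS". Section 17 ties the size to feasibility ("we chose a sample size of 20") and gives no power calculation. The only threshold is in Section 17, for comparisons at the study time points: "a p value<0.05 will be considered significant".

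Solicited side effects are handled elsewhere. Section 4, secondary outcome 7, scores seven symptoms 0 to 10 after each session (total 0 to 70). As continuous data, that score would fall under the t-test in Section 17.

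**The concern.** A per-event significance test in 20 subjects can hardly ever reject. If it is the only formal comparison, nearly every adverse event will come out non-significant whatever the true difference, and the result will not show how large an excess remains possible. That matters most for the serious events. Four suicide attempts or hospitalizations on active against none on sham would be non-significant under this rule.

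The pilot is also meant to feed a full randomized trial (Section 1, Hypothesis 2). A p-value above 0.05 gives that trial's safety planning nothing to use; an interval does. This is separate from false positives among the efficacy comparisons, and adjusting those comparisons would not address it.

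**Working it through.** **Inputs.** From the documents: Fisher's exact test on subjects with at least one event (Section 16); N = 20 and 1:1 allocation, so 10 v 10 (Sections 4 and 4.1); all subjects included, so no deduction for dropout (Section 16). Assumed: two-sided 0.05, borrowed from Section 17 because Section 16 gives no level, and an exact 10/10 split. For event rates, 41% and 68% are the itching and tingling figures that Section 4.1 quotes from other trials ("a similar proportion of tingling (68%), itching (41%), and warmth sensation (42%) between active and sham groups"). The 10% and 40% rates are illustrative, and 82% is twice 41%. The plan states no power or detectable difference for these tests, so there is no figure of its own to reproduce.

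**Rejection region.** When one arm has no events, the two-sided p-value for k v 0 at 10 per arm is 2 × C(10,k) / C(20,k).

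- 4 v 0: 2 × 210 / 4845 = 0.087
- 5 v 0: 2 × 252 / 15504 = 0.033

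By symmetry (counting non-events), 10 v 6 equals 4 v 0, so p = 0.087. 10 v 7 equals 3 v 0: 2 × 120 / 1140 = 0.21. Enumerating all 11 × 11 tables gives:

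| Sham count (of 10) | Smallest active count with p<0.05 | p |
|---|---|---|
| 0 | 5 | 0.033 |
| 1 | 7 | 0.020 |
| 2 | 8 | 0.023 |
| 3 | 9 | 0.020 |
| 4 | 10 | 0.011 |
| 5 | 10 | 0.033 |
| 6 or more | none | 0.087 or higher |

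Near the 41% rate (about 4/10 on sham), 9 v 4 gives p = 0.057 and is not flagged.

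**Size and power.** For true rates p1 (active) and p0 (sham), sum Bin(a; 10, p1) × Bin(b; 10, p0) over all tables (a, b) with p<0.05.

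- Actual two-sided size: 0.1% at 10%; 1.3% at 41%.
- Power: 6% for 10% v 30%; 15% for 10% v 40%; 27% for 41% v 82%.
- At a 68% sham rate, the chance of 6 or more sham subjects with the event is 81%, and then no active count can be flagged. Even if all active subjects have the event, power is 19%.

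**Sensitivity to the assumptions.** One-sided, 4 v 0 and 10 v 6 each give p = 0.043. With 9 active and 11 sham, two-sided 4 v 0 gives p = 0.026. With 11 active and 9 sham, 5 v 0 is needed (p = 0.038). The boundary moves by about one subject.

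**What intervals would show.** The Newcombe interval combines the two Wilson intervals. For 4/10 v 0/10 these are 0.168 to 0.687 and 0 to 0.278.

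- Lower limit: 0.40 - √((0.40 - 0.168)² + 0.278²) = 0.04
- Upper limit: 0.40 + (0.687 - 0.40) = 0.69

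The report would be +40 points (95% CI 4 to 69). For 10/10 v 7/10 it is +30 points (-4 to 60). For 0/10 the Clopper-Pearson upper limit is 1 - 0.025^(1/10) = 0.308, so zero events in an arm is compatible with a true rate up to 31%.

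**The case against.** Fisher's test is a valid choice for sparse 2 × 2 tables, and the low power comes from n = 20, not from the test. The trial is sized for feasibility and has no safety hypothesis. No decision depends on the Fisher result: Section 16 assesses each event individually for intensity, course and causality, and Section 9 has its own session-level safeguards. The per-arm counts that the test needs would let any reader compute an interval. All of this stands, and it limits the point to one about reporting.

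Four stronger readings are tempting, and the documents do not support them.

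- A reader might infer that common events can never be flagged. That holds only when 6 or more sham subjects are affected. At a 41% sham rate the chance of that is 18%, and 10 v 4 or 10 v 5 is flagged.
- A reader might infer that harms have no other between-arm comparison. The solicited 0 to 70 score is compared under Section 17. It includes itching but not tingling, and nothing says solicited sensations are also coded as adverse events, so the 41% and 68% rates serve only as examples here.
- A reader might infer that the investigators will report equal safety from non-significance. No passage says so. It is a risk, because nothing rules it out.
- A reader might infer that intervals cure the lack of information. They do not: no Newcombe interval shows an excess once 7 or more sham subjects have the event. Newcombe also excludes zero more often than Fisher rejects when there is no difference (about 4.1% v 1.3% at 41%; 0.9% v 0.1% at 10%), which would add chance signals across many event types if the intervals were used as tests.

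**Conclusion.** The concern holds as a point about analysis and reporting of adverse events, and a change is worth making. Unless the excess on active is extreme, the planned test will be non-significant, so its result cannot distinguish equal safety from a large excess. The exact boundary rests on a two-sided 0.05 level and a 10/10 split, neither fixed by Section 16. Changing either shifts the cut-offs slightly and leaves the conclusion intact, because no variant supplies an estimate or an interval. The trial's case-by-case safety handling and its solicited side-effect score are not in question.

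**What to change.** Amend Section 16 as follows.

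- For each adverse event, make the main report n/N per arm with exact (Clopper-Pearson) 95% intervals, and the active-minus-sham risk difference with a Newcombe 95% interval.
- Keep any Fisher p-values as descriptive only, and state their level and sidedness.
- State that a non-significant result will not be taken as evidence of equal safety, and that the intervals are descriptive and not a set of tests.

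The cost is a sentence or two and a few lines of code, with no new data, visits or subjects. The downside is that the intervals will be wide and, given the higher exclusion rate of the Newcombe interval, some will exclude zero by chance when many event types are listed.
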